#### Statistical Analysis Plan

Page 42 of 78

3	3		
Score Range – 0 to 13	Score Range – 0 to 13	Score Range – 0 to 11	Score Range – 0 to 11

The overall ultrasound score is calculated by summation of the grades for the 5 above mentioned parameters - for all 4 major salivary glands. The overall ultrasound score can range from 0 to 48.

If any parameter is not assessed, the whole score cannot be derived, no substitutes for missing data.

Responder for salivary gland function has two components:

- UWSF: at least 25% increase in score, or if score is 0 mL/min at baseline, any increase from baseline OR
- SGUS: at least 25% decrease in total Hocevar score from baseline

Unstimulated whole salivary flow (UWSF) will be measured as ml per minute.

#### 5) Serology: It is measured with serum IgG and RF

For the biological domain, levels of rheumatoid factor (RF), and IgG are measured based on blood sample examined in the laboratory. TThe amount of RF antibody will be measured in - (IU/ml) [ (IU/ml] and IgG will be assessed in (g/L).

A responder for biological domain is defined as follows:

- $\circ$  A response is defined as  $\geq 10\%$  reduction in IgG from baseline or
- o A response is defined as  $\geq 25\%$  decrease in rheumatoid factor (RF) from baseline

#### Primary Analysis

Main Estimand Strategy: This is based on a composite endpoint strategy. This estimand is intended to provide an estimate of the treatment effect in the absence of prohibited concomitant medication use in a population without treatment discontinuation.

Analysis methodology: The test of proportions will be conducted at a two-sided level alpha of 0.05 with no adjustment for multiplicity. Based on the CRESS response, participants will be categorized as responders versus non-responders and a 95% Wilson Score CI for the proportion of CRESS responders will be presented for both treatment groups.

The proportion of responders and its 95% Wilson score CI will be calculated using binomial distribution. To perform this in SAS,

Document:

Author:

Version Number:

Version Date:

31JAN2024

Template No.: CS TP BS016 Revision 7

[figure not shown]
Reference: CS WI BS005

Effective Date: 01Nov2021

Statistical Analysis Plan

Page 43 of 78

The common odds ratio will be provided, along with the 95% CI. For above analysis, in the event of missing values for the primary endpoint, assessments on or after ICEs will be treated as Non-Responders as per primary estimand composite strategy.

Intercurrent events Data after study drug discontinuation and prohibited concomitant medication will be excluded and set to missing.

Missing Data not related to intercurrent events: There will be no imputation performed on missing data, not related to intercurrent events.

Document: Author: Version Number: V2.0

31JAN2024

Version Date:

Template No.: CS\_TP\_BS016 Revision 7 Reference: CS WI BS005

Effective Date: 01Nov2021

Statistical Analysis Plan

Page 44 of 78

Here, the numerator will include participants which are responders. Participants who are taking prohibited concomitant medications or early discontinue study treatment, are considered as Non-Responders. The denominator will include all participants irrespective of any ICEs occurred.

Supplementary Estimand Strategy: This is based on hypothetical strategy. Any early discontinuation or taking prohibited concomitant medication is observed- then the assessment will be set to missing and the missing binary outcomes will be imputed, assuming that they are missing at random. The aim of hypothetical strategy is to address the effect in an alternative hypothetical setting where subject neither discontinued or no prohibited concomitant medication available.

Analysis set: Efficacy Analysis set.

Analysis Methodology:

The SAS procedure MI will be used and the details of MI procedure will be stated in the dataset specification document. The missing binomial outcomes will be imputed by multiple imputation method with the assumption of monotone missing pattern and logistic regression method. Multiple imputations would be conducted based on CRESS response (Yes/No). To reduce the sampling variability from the imputation process, 500 datasets will be generated.

Here in this case the numerator will include all the participants which are responders (imputed and actual responders) and the denominator will include all participants in FAS population.

In the estimation step, separate analysis will be performed using the statistical method mentioned for the primary endpoint statistical analysis.

Because the imputation of missing data is a key aspect to the analysis of the data, explicit details regarding this imputation are provided via sample SAS code that is intended to demonstrate the application of these strategies. Minor alterations to SAP code may be performed.

Example code for imputation of binary outcome which will be used for imputation by logistic regression is as follows:

Document:

Author:

Version Number:

V2.0

Template No.: CS TP BS016 Revision 7

Version Date: 31JAN2024

[figure not shown]
Reference: CS WI BS005

Effective Date: 01Nov2021

Statistical Analysis Plan

[figure not shown]
Page 45 of 78

Statistical Analysis Plan

Page 46 of 78

[figure not shown]

Effective Date: 01Nov2021

Statistical Analysis Plan

Page 47 of 78

The values obtained from back transformed dataset, will be used for reporting Unadjusted Odds Ratio and CIs.

If the planned hypothetical approach is not feasible due to data sparsity, then available data occurring on or after ICEs will be analyzed as observed (treatment policy). In this case, the numerator will include all the participants which are responders (actual responders only) and the denominator will be participants in EAS population.

Missing data unrelated to ICEs, will not be imputed.

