The primary estimand for the study is the proportion of CRESS responders on ≥ 3 of 5 items at week 24 in efgartigimod IV compared to placebo, considering the participant who discontinued study treatment or used any prohibited	Efgartigimod or placebo, taking into account study treatment discontinuation and/or prohibited concomitant medication.	Efgartigimod or placebo in the scenario where study treatment discontinuation and/or prohibited concomitant medication would not have occurred.
medications.	Population  Adult participants with pSS, per ACR/EULAR 2016 classification criteria, with at least a moderate level of systemic disease activity (ESSDAI ≥ 5) as defined by Inclusion and Exclusion criteria.	Population  Adult participants with pSS, per ACR/EULAR 2016 classification criteria, with at least a moderate level of systemic disease activity (ESSDAI ≥ 5) as defined by Inclusion and Exclusion criteria.
	Variable (endpoint)Proportion of CRESS responders on ≥ 3 of 5 items at week 24.	Variable (endpoint)  Proportion of CRESS responders on ≥ 3 of 5 items at week 24.

Document:

Author: Version Number: V2.0

Version Date: 31JAN2024
Reference: CS\_WI\_BS005

Effective Date: 01Nov2021

Template No.: CS\_TP\_BS016 Revision 7

Statistical Analysis Plan

Page 17 of 78

Intercurrent events (Composite Variable Strategy)  • Early withdrawal of study treatment • Use of any prohibited concomitant medications	Intercurrent events (Hypothetical Strategy strategy).  • Early withdrawal of study treatment • Use of any prohibited concomitant medications
Summary measure  The proportion of responders and its 95% Wilson score CI will be calculated using binomial distribution for treatment and placebo. Also, CMH will be used  The participants with ICEs will be considered as Non-Responders.	Summary measure  The proportion of responders and its 95% Wilson score CI will be calculated using binomial distribution for treatment and placebo. Also, CMH will be used.  If the planned hypothetical approach is not feasible due to data sparsity, then data will be analyzed as observed.

Abbreviations: ICE= Intercurrent Event, CI= Confidence Intervals.

Where the strategies are described as follows in the sequence, these strategies will be applied:

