#### For the Main estimand:

Composite Variable strategy: Assessment on or after ICEs will be treated as Non responder. The rationale behind composite strategy is, discontinue of study treatment or use of prohibited concomitant medications will affect the CRESS response.

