## 3.4. Changes to Analysis from Protocol

- For this SAP, Estimand are defined for the study in Table B. The primary estimand for the study is to
  assess the proportion of CRESS responders on ≥ 3 of 5 items at week 24 in efgartigimed IV compared to
  placebo, considering the participant who discontinued study treatment or used prohibited concomitant
  medication.
- The histology of the parotid gland (Immunohistochemistry- The relative counts of lymphocytic infiltrate (stained for CD45), B/B+T cell ratio) will be considered as – Exploratory endpoint and not as secondary endpoint.

- 4. Data for the following biomarker endpoints will be received and processed by the sponsor:
  - a. Autoantibodies in serum including Anti-Ro/SS-A and Anti-La/SS-B
  - c.
  - d.

Document:

Author:

Version Number:

V2.0

Version Date:

31JAN2024

[figure not shown]
Template No.: CS TP BS016 Revision 7 Reference: CS WI BS005

Effective Date: 01Nov2021

Statistical Analysis Plan

Page 22 of 78

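### SAP 14.1.1 gives the composite primary estimand a hypothetical aim, and sets a FAS denominator for a supplementary imputation analysis that it assigns to the EAS

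*SAP*

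**What the plan says.** **Main estimand.** In SAP Section 2, Table B lists a composite variable strategy for early withdrawal of treatment and use of prohibited medication. It gives the treatment condition as "Efgartigimod or placebo, taking into account study treatment discontinuation and/or prohibited concomitant medication". The text under the table adds: "Assessment on or after ICEs will be treated as Non responder". SAP Section 3.4 describes the primary estimand in the same spirit, "considering the participant who discontinued study treatment or used prohibited concomitant" medication. Section 14.1.1 repeats the composite label, but states the aim as "an estimate of the treatment effect in the absence of prohibited concomitant medication use in a population without treatment discontinuation".

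On handling, Section 14.1.1 says that "in the event of missing values for the primary endpoint, assessments on or after ICEs will be treated as Non-Responders". It then says: "Intercurrent events Data after study drug discontinuation and prohibited concomitant medication will be excluded and set to missing". A little later in the same subsection it states that participants with either event are non-responders, and that the denominator holds all participants whether or not an event occurred.

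**Supplementary estimand.** Table B defines this as the effect "in the scenario where study treatment discontinuation and/or prohibited concomitant medication would not have occurred". Section 14.1.1 names the EAS as the analysis set. The planned analysis is multiple imputation, with all FAS participants as the denominator. If sparse data make imputation infeasible, the fallback analyses the data as observed, with the EAS as the denominator.

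**Sets.** SAP Section 5.4 defines the EAS as those FAS participants who are eligible for efficacy evaluation on pre-randomization information. SAP Section 14.1 puts the primary efficacy analyses on the EAS.

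**The concern.** The two estimands differ in what they do with events: one counts them as failures, and the other asks what would have happened without them. Section 14.1.1 gives both the second aim. A report that follows the SAP's sentence would present a rate with discontinuers scored as failures as if it described a world without discontinuation. Protocol Section 9.1 sets effect estimation, with no formal hypothesis, as the focus, so what the estimate means is the main product of the trial.

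The denominator conflict affects comparison of the main and supplementary results. They are meant to differ only in how events are handled. If one is on the EAS and the other on the FAS, they can also differ in population, and a programmer working from EAS data could divide EAS responders by the FAS count.

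**Working it through.** **1. Aim against rule, main estimand**

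| Place in SAP | What it implies for events |
|---|---|
| Table B, main, treatment condition | Events taken into account |
| Table B, main, summary measure | Events are non-response |
| Section 2, text on main estimand | Events are non-response |
| 14.1.1, numerator and denominator | Events are non-response; everyone kept |
| 14.1.1, stated aim | Events absent; population without discontinuation |
| Table B, supplementary, treatment condition | Events would not have occurred |

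The stated aim matches the last row and none of the first four. The error lies in the description; the rule is consistent.

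To show how far apart the two quantities can be, assume 20 efgartigimod participants, k of them with an event, a 50% response rate among the rest, and imputation that gives those with events the same rate.

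- Composite rate = 0.5 × (20 − k) / 20. Hypothetical rate = 50.0%.
- k = 2: 9/20 = 45.0% against 50.0%, a gap of 5 points.
- k = 4: 8/20 = 40.0% against 50.0%, a gap of 10 points.

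These gaps show what a reader would misinterpret. They are not errors in the computed primary rate. The value of k is assumed; the documents give none.

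**2. Precision for scale**

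The plan's own figure (Protocol 9.5, SAP 3.2) is a one-sided 95% Wilson lower bound of about 33% for 10 responders of 20. With p = 0.5, n = 20, z = 1.645:

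lower = [p + z²/(2n) − z√(p(1−p)/n + z²/(4n²))] / (1 + z²/n) = (0.5677 − 0.1960) / 1.1353 = 0.327.

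That is 32.7%, so the figure is reproduced. The two-sided 95% interval (z = 1.960) is 29.9% to 70.1%.

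**3. Denominator, supplementary estimand**

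| Item | Set |
|---|---|
| Primary efficacy analyses (14.1) | EAS |
| Supplementary analysis set line (14.1.1) | EAS |
| Multiple-imputation denominator (14.1.1) | FAS |
| As-observed fallback denominator (14.1.1) | EAS |

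The third row is the only one out of line. For illustration, assume FAS = 20, EAS = 18 and 10 responders in the EAS, counting actual and imputed responders.

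- EAS rate: 10/18 = 55.6% (two-sided Wilson 33.7% to 75.4%).
- FAS rate, neither of the 2 others a responder: 10/20 = 50.0%.
- FAS rate, both others responders: 12/20 = 60.0%.

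The FAS denominator therefore moves the rate by −5.6 to +4.4 points. If EAS = FAS, the shift is zero.

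**The case against.** **No result changes under the aim sentence.** The non-responder rule is stated in Table B, in the text of Section 2 and in Section 14.1.1, so the programming would be right. This stands, and it limits the severity. It does not rescue the sentence. One could read the aim as response reached without an event, but a population without discontinuation does not fit a denominator that keeps discontinuers.

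**The two denominators belong to different branches.** The FAS goes with the imputation and the EAS with a fallback used only if imputation is infeasible, so this is not one calculation with two denominators. That is correct. The conflict is between the imputation branch and the analysis set named for that same supplementary analysis.

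**The sets may coincide.** EAS exclusions rest on pre-randomization information, Protocol Section 5 permits no enrollment waivers, and SAP Section 5 fixes membership before unblinding. The documents give no EAS size, so the practical effect may be nil.

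**A stronger reading that does not hold.** A reader might infer that setting post-event data to missing, together with the rule in SAP Section 7.2 that leaves missing values out of percentages, drops participants with events from the primary denominator. Section 14.1.1 rules this out: it scores those participants as non-responders and keeps everyone in the denominator regardless of events. That endpoint-specific rule governs over the general output rule.

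**Two further inferences to avoid.** The use of the EAS where Protocol Section 9.2 names the FAS cannot be called unexplained, because the list of changes in SAP Section 3.4 is incomplete in the public copy. Nor is missing week-24 CRESS unrelated to events a contradiction. The main analysis says "There will be no imputation performed on missing data, not related to intercurrent events", and Protocol Section 9.3.2 limits the primary analysis to participants with a week-24 value, but Section 14.1.1 does not spell out the denominator. That calls for clarification only.

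**Conclusion.** Two statements in SAP Section 14.1.1 are wrong as written, at minor to moderate severity.

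- The aim given for the composite main estimand is that of the hypothetical supplementary estimand. The computed primary rate is unaffected; its interpretation is not. The two targets would differ by 5 points with 2 events in 20 and by 10 points with 4, under the assumptions shown.
- The imputation branch takes a FAS denominator against its own EAS analysis set, the EAS fallback and the EAS primary analysis. Under the assumed counts the rate is 50.0% to 60.0% in place of 55.6%. This is small beside an interval about 40 points wide, and zero if the sets coincide.

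No decision threshold is crossed. The conclusions rest on the visible SAP text and not on the code missing from the public copy.

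**What to change.** 1. In Section 14.1.1, restate the main aim as the effect on CRESS response at week 24 achieved without treatment discontinuation or prohibited medication, with either event counted as non-response.
2. For consistency, reword the sentence that excludes post-event data and sets them to missing, so that it says these participants are scored as non-responders, as the subsection already provides.
3. Use the EAS for the multiple-imputation denominator, matching the primary and fallback analyses. A FAS result may be reported in addition.
4. As a clarification, add one sentence on how week-24 CRESS missing for reasons unrelated to events enters the primary and imputation denominators.

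The cost is a few lines of SAP text. No new data are needed, and any FAS result is an optional extra table.

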#### 14.2. Secondary Efficacy

The secondary efficacy analyses will be performed for the EAS and will be analyzed on data observed.

#### 14.2.1. Secondary Efficacy Variables & Derivations & Analyses.

# 14.2.1.1 Proportion of Participants with Minimal Clinically Important Improvement in ESSDAI: Iimprovement of $\geq$ 3 Points in ESSDAI Score at Week 24 and Proportion of Participants with Low Disease Activity: ESSDAI Score of < 5 at Week 24

As explained in Section 14.1.1, the ESSDAI (Seror [a], et al., 2015) consists of 12 domains, 11 related to organ involvement (cutaneous, pulmonary, renal, articular, muscular, peripheral nervous system, central nervous system, hematological, glandular, constitutional, and lymphadenopathic) and 1 biological domain reflecting B-cell activity.

Document:

Author:

Version Number:

V2.0

Version Date:

31JAN2024

Template No.: CS TP BS016 Revision 7 Reference: CS WI BS005

Effective Date: 01Nov2021

Statistical Analysis Plan

Page 48 of 78

Table G: Domain Weights of ESSDAI

Domain (activity level)	ESSDAI Weights
Constitutional (0-2)	3
Lymphadenopathy (0-3)	4
Glandular (0-2)	2
Articular (0-3)	2
Cutaneous (0-3)	3
Pulmonary (0-3)	5
Renal (0-3)	5
Muscular (0-3)	6
Peripheral nervous system (0-3)	5
Central nervous system (0-3)	5
Hematological (0-3)	2
Biological (0-2)	1
Score total	0-123

Each domain is scored on a range of values depending on their activity level, which can include 3 or 4 levels, into a scale from 0: No, 2: Moderate, 3: High.t

For ESSDAI, the activity levels of each domain (range: 0-3 points or 0-2 points) are multiplied by their respective weights (range: 1-6 points) to obtain the total score. The final score, the sum of all domain scores, falls between 0 (no disease activity) and, theoretically, 123 (higher disease activity). ESSDAI cannot be assessed if any domain is missing.

The Biological domain for post baseline visits will be derived using following variables at analysis level:

 Document:
 Version Number:
 V2.0

 Author:
 Version Date:
 31JAN2024

 Template No.:
 CS\_TP\_BS016 Revision 7
 Reference:
 CS\_WI\_BS005

Effective Date: 01Nov2021

#### Statistical Analysis Plan

Page 49 of 78

Biological [1]	No=0	Absence of any of the following biological features
	Low=1	Clonal component and/or hypocomplementemia (low C4 or C3 or CH50) and/or hypergammaglobulinemia or high IgG level between 16 and 20 g/L
	Moderate=2	Presence of cryoglobulinemia and/or hypergammaglobulinemia or high IgG level > 20 g/L, and/or recent onset hypogammaglobulinemia or recent decrease of IgG level (< 5 g/L)

The proportion of efgartigimod and placebo participants with improvement of >= 3 points in score and the proportion of participants having ESSDAI score of <5 at week 24 will be provided, along with 95% Wilson Score CIs by each IgG stratum at screening (> 16.0 g/L or  $\leq$  16 g/L) for both treatment groups and for each of these two endpoints.

# 14.2.1.2 Proportion of Participants with Minimal Clinically Important Improvement in clinESSDAI: Improvement of ≥ 3 Points in clinESSDAI Score at Week 24 and Proportion of oParticipants with Low Disease Activity: clinESSDAI score of < 5 at Week 24

As explained in Section 14.1.1 of SAP, the ClinESSDAI includes all ESSDAI domains except the biological domain.

The proportion of efgartigimod and placebo participants with improvement of  $\geq$  3 points in clinESSDAI score and the proportion of participants having clinESSDAI score of  $\leq$  5 at week 24 will be provided, and along with 95% Wilson Score CIs by each IgG stratum at screening ( $\geq$  16.0 g/L or  $\leq$  16 g/L) for both treatment groups and for each of these two endpoints.

### 14.2.1.3 Proportion of Participants with Minimal Clinically Important Improvement in ESSPRI: Decrease of 1 Point or ≥ 15% at Week 24

The Information on the derivation of ESSPRI total score is provided in Section 14.1.1.

The proportion of participants with decrease of 1 point or  $\geq$  15% in ESSPRI total score at week 24 will be provided and along with 95% Wilson Score CIs by each IgG stratum at screening ( $\geq$  16.0 g/L or  $\leq$  16 g/L) for both treatment groups and for each of these two endpoints.

#### 14.2.1.4 Change in ESSDAI Score, clinESSDAI Score and ESSPRI Score at Week 24

These scores will be descriptively summarized for actual scores and changes from baseline scores for each visit and by treatment.

Document:

Author:

Version Number: V2.0

Version Date: 31JAN2024

Template No.: CS TP BS016 Revision 7 Reference: CS WI BS005

Effective Date: 01Nov2021

Statistical Analysis Plan

Author:

Template No.: CS\_TP\_BS016 Revision 7

Effective Date: 01Nov2021

Page 50 of 78

For change from baseline to week 24 for ESSDAI, clinESSDAI and ESSPRI scores, between treatment group
difference will be analyzed using longitudinal mixed model repeated measures (MMRM).
To estimate the difference between the efgartigimod and placebo in mean change from baseline to Week 24, a
treatment-by-visit interaction contrast will be constructed (i.e., the treatment group contrast at Week 24). On the
basis of this analysis, LS means, SE with 95% CI for placebo and efgartigimod will be reported, along with
difference in LS means of efgartigimod vs placebo (with SE), 95% 2-sided CI. 2-sided p-value for testing
differences between treatment groups will also be presented. Inference will be based on the precision of the
Document:

Copyright © 2009, 2010, 2012, 2016, 2018, 2019, 2021 IQVIA. All rights reserved. The contents of this document are confidential and proprietary to IQVIA Holdings Inc. and its subsidiaries. Unauthorized use, disclosure or reproduction is strictly prohibited.

Version Number:

Reference: CS\_WI\_BS005

Version Date:

V2.0

31JAN2024

Statistical Analysis Plan

Page 51 of 78

estimation rather than hypothesis testing.

#### 14.2.1.6 Proportion of Participants with STAR Score of ≥ 5 at Week 24

STAR has been developed to assess the efficacy of treatments for pSS.

The details of each of the components remains the same as explained in Section 14.1.1. This composite measure contains 5 domains (like CRESS):

- Systemic activity: If participant has clinESSDAI score decreased by ≥ 3 points at week 24, in that case the
  participant will be scored with 3 points
- Patient-reported outcome: If participant has ESSPRI score decrease of at least 1 point or ≥ 15% at week 24, in that case the participant will be scored with 3 points
- Lacrimal gland function (assessed by Schirmer's test or OSS)

Here there are two criteria associated w.r.t Schirmer's test:

- If Schirmer's test is ≤5 mm at baseline (abnormal) in at least 1 eye, a response is defined as an increase of at least 5 mm from baseline.
- If Schirmer's scores are normal in both eyes at baseline, a response is defined as no change to abnormal.

Also, there are two criteria associated w.r.t OSS:

- If OSS score ≥ 3 points at baseline (abnormal) in at least 1 eye, a response is defined as a decrease of at least 2
  points from baseline.
- If OSS scores are normal in both eyes at baseline, a response is defined as no change to abnormal.

If either of the Schirmer's test or OSS assessment criteria are met, 1 point is assigned.

 Document:
 Version Number:
 V2.0

 Author:
 Version Date:
 31JAN2024

 Template No.:
 CS\_TP\_BS016 Revision 7
 Reference:
 CS\_WI\_BS005

Effective Date: 01Nov2021

Statistical Analysis Plan

Page 52 of 78

• Salivary gland function

Here there are two criteria associated w.r.t UWSF:

- If score > 0 at baseline: increase of  $\ge 25\%$  from baseline
- If score is 0 at baseline: any increase in UWSF from baseline

OR

SGUS: ≥ 25% decrease in total Hocevar score from baseline

If either of the UWSF or SGUS assessment criteria are met, 1 point is assigned.

[figure not shown]
- Biological (assessed by IgG or RF): 1 point is assigned if,
  - IgG: ≥ 10% reduction
  - RF:  $\geq$  25% decrease

The proportion of participants with STAR score of  $\geq$  5 points at week 24 will be provided and along with 95% Wilson score CIs by each IgG stratum at screening ( $\geq$  16.0 g/L or  $\leq$  16 g/L) for both treatment groups and for this endpoint in an identical manner to the primary endpoint.

